### Introduction

[figure not shown]
Preterm birth is a leading global cause of neonatal mortality despite of numerous advances and intensive research in perinatal medicine. Almost one million children die each year due to complications of preterm birth and in almost all countries with reliable data, preterm birth rates are increasing. Of the 14 million survivors per year, many face a lifetime of disability, including learning disabilities, visual and hearing impairments.

Preterm birth occurs for a variety of reasons. The majority of preterm births happen spontaneously, though some are due to early induction of labor or caesarean birth, typically due to for medical maternal or neonatal conditions. Common causes of spontaneous preterm delivery (SPTD) include multiple pregnancies, infections, chronic conditions, lifestyle, family history, cervical incompetence; however, often no one cause is identified. Although SPTD is often a multifactorial event, precocious cervical softening, shortening and dilatation are a common denominator.

The uterine cervix has to provide structural integrity and mechanical resistance to ensure normal development of the fetus as the uterus expands to accommodate the fetus' growth. Preterm delivery is closely related to a premature cervical ripening. The scientific basis for the proposed project is that the elasticity modulus of a cervix is a more sensitive parameter characterizing the stage of cervical ripening. The main component of the cervix tissue is collagen. Cervical ripening is the result of realignment of collagen, degradation of collagen cross-linking due to proteolytic enzymes. These processes affect the elasticity modulus of the cervical tissue. Therefore, assessment of cervix by a device measuring cervical elasticity (stiffness) and cervical length (effacement) appears to be an adequate approach for identifying pregnant women at high risk of SPTD.

The primary cervical elasticity assessment currently used in clinical practice is relying on the clinician's evaluation of the cervix as "hard, medium or soft" which is descriptive and subjective. Clinicians use terms such as *softening*, *shortening*, *funneling*, *effacing*, and *dilating* to describe changes in the cervical conditions that occur during pregnancy. Collectively, these changes are called *cervical remodeling* and refer to both the tissue's intrinsic material property changes and its resultant anatomical changes. These changes definitely require objective and reliable quantification.

In the scope of this project we propose to develop and clinically validate a new and cost-effective device, Cervix Monitor (CM), for detecting cervix conditions leading to SPTD and its risk assessment. The CM will be based on measuring of the applied pressure to the cervix by a tactile sensor array (stress data) and ultrasound measurement of cervix length (strain data). Tactile and ultrasound sensors will be allocated on the tip of the disposable measuring part of vaginal probe (see Figure 1). Both stress and strain data will allow cervix elasticity and effacement evaluation. The discovery of novel biomarkers that could reliably identify women who will subsequently deliver preterm, may allow for timely medical intervention and targeted therapeutic treatments aimed at improving maternal and fetal outcomes.

**Figure 1.** Concept of proposed cervix monitor. It will allow elasticity and length measurements of the uterine cervix during gestation to explore and detect conditions leading to spontaneous preterm delivery.

The objectives of the Phase I research, which covers the proposed protocol, are listed below.

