### Sample Size

The study will involve 10 remunerated subjects.

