## **Methods and Procedures**

The examination procedure will comprise the steps of:

1. Inserting the speculum into the vagina to provide appropriate visualization and access to the cervix.
2. Performing CM measurements at 3, 6, 9, and 12 o'clock specifying the probe tip location on cervix on the touch screen display.
3. Review the measurement results (elasticity and length values) and repeat two measurements, one at the location with the lowest elasticity and one at the location with highest value.
4. Removing the probe and speculum from the vagina.

This CM examination procedure will be explored and further optimized based on the practical experience.

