## **Study End Points**

Study end points (measures that will be considered as success):

1. The examination using CM is safe, does not cause significant discomfort and is capable of production of expected measurement results.
2. The CM elasticity measurements have intraoperator ICC of 0.90 or above; 95% LOA is within  $\pm 15\%$ .
3. The CM cervix length measurements have intraoperator ICC of 0.93 or above; 95% LOA is within  $\pm 10\%$ .

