#### Protection Against Risks

All investigators performing the CM examination will receive appropriate training in order to negate the lack of familiarity with the device. The risk of physical damage to the vagina and cervix will be minimized by utilization of standard procedure to assess the cervix using a speculum. A physical contact of the probe tip with the cervix surface will be detectable by a tactful feedback from the CM probe. The risk of cross-contamination and infection will be

eliminated by the use of disposable (single use) probe shaft which be sterilized and stored in a sterile sheath before the clinical use. It is highly unlikely that the use of the CM probe can produce any toxicity since the probe shaft is made of certified biocompatible.

Software and hardware malfunction risks are minimized by completion of full component and system testing cycle prior to the initiation of the clinical study. The devices will go through performance bench testing on simulator models to verify proper CM functionality. Standard software verification and validation procedures mitigate the risk of incorrect characterization being presented to the user during the patient examination. All participating clinical investigators will be trained to recognize inappropriate software and hardware behavior and to react on it.

Possible risks to the patient caused by electrical shock are negligible due to absence of supplied voltage to the probe, to protective features of electronics and isolated medical-grade power supply to electronics and computer. The device will go through a full cycle of EMC and electrical safety testing at an independent certified test facility. If ordered by local IRB, the device will be also tested by appropriate hospital personnel responsible for biomedical safety.

To protect against the risk of breach of confidentiality, patient confidentiality will be maintained at all times. The record of patient's progress while on this study will be kept in locked file cabinets to which only limited research staff will have access. The confidentiality of any central computer record will be carefully guarded, and no information by which patient can be identified will be released or published. All information on the case report forms or any information communicated from clinics to the company will be de-identified. The psychological risk will be minimized by the fact that no change in clinical diagnosis and patient management will result from this study.

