#### Importance of the Knowledge to be Gained

The proposed clinical studies in the first exploratory stage of the project will allow to assess potential risks of CM to pregnant women in studies with non-pregnant women, to develop and test the data collection technique and establish possible limitations in the CM use, to assess CM measurement reproducibility, evaluate the probe ergonomic design and ease of use, and to assess the clinical suitability of the interface software to facilitate the data collection process and to get *in vivo* test data for off-line development of analysis routines. After meeting the basic research milestones in the exploratory stage, we plan extensive clinical studies on pregnant patients to obtain quantitative data on changes of cervix elasticity for the months of pregnancy, on estimating the level of the cervix softening which may qualify the patient for a medical treatment and on the range of variability of cervix stiffness which need to be taken into account while making decisions on clinical intervention.

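### If the sensors are on the single-use part, end points 2 and 3 can show only same-probe, same-insertion repeatability, not reproducibility across probes or visits

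*Combined protocol and SAP*

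**What the plan says.** The Introduction describes the device: "Tactile and ultrasound sensors will be allocated on the tip of the disposable measuring part of vaginal probe". Protection Against Risks controls cross-contamination by the "use of disposable (single use) probe shaft".

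Methods and Procedures takes readings at four clock positions. The operator then reviews them and is to "repeat two measurements, one at the location with the lowest elasticity and one at the location with highest value". Only after that comes the last step, "Removing the probe and speculum from the vagina". First and repeat readings at a site therefore fall within one insertion.

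Data Analysis computes an ICC, defined as the correlation between two measurements on one woman, and Bland-Altman 95% LOA from the paired differences. Study End Points sets success for elasticity as "The CM elasticity measurements have intraoperator ICC of 0.90 or above" with LOA within ±15%, and for length as an ICC of at least 0.93 with LOA within ±10%.

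The stated purpose varies by section. Study Objectives and Data Analysis speak of repeatability, and the end points are labelled intraoperator. Importance of the Knowledge to be Gained says that this stage is "to assess CM measurement reproducibility" and looks ahead to tracking elasticity over the months of pregnancy.

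**The concern.** If the disposable measuring part and the single-use shaft are the same component, the first woman is read with the first sensor set, the second woman with the second, and so on. A calibration offset in one probe is common to both readings of that woman. It drops out of the paired difference, so the LOA do not see it. It also makes women look more different from one another, so the ICC rises. Less consistent probes would score better on one success criterion and lose essentially nothing on the other.

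The planned use is longitudinal. With single-use sensors, every comparison between visits compares two probes as well as two dates. Success on end points 2 and 3 could then be read as reproducibility of the device, when the design leaves the probe-to-probe component unmeasured. Bench testing is planned, but only to confirm that the device works. No probe-to-probe tolerance is stated, and nothing links a bench reading to the probe used in a given woman.

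**Working it through.** There is no stated power or sample-size calculation to reproduce. Sample Size says only "The study will involve 10 remunerated subjects", and the ICC and LOA limits are criteria, not derived figures.

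**Model.** Reading = true value (between-woman SD *b*) + probe effect (SD *s*) + repeat error (SD *w*), all as percent of the mean.

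- Same probe for both readings, a new probe per woman (the plan): ICC = (b² + s²)/(b² + s² + w²); LOA = ±1.96·√2·w.
- One common probe for all women: ICC = b²/(b² + w²).
- A different probe for each reading: ICC = b²/(b² + s² + w²); LOA = ±1.96·√(2(w² + s²)).

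**Inputs.** The ICC and LOA limits come from Study End Points. The documents give no value for *s*, so it is assumed at 2%, 5% and 10%.

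**Elasticity, results exactly at the limits.** w = 15/(1.96·√2) = 5.41%. ICC 0.90 implies b² + s² = w² × 0.90/0.10, so √(b² + s²) = 16.23%. At s = 5%, b² = 263.6 − 25 = 238.6 and the total variance is 263.6 + 29.3 = 292.9. The across-probe ICC is 238.6/292.9 = 0.815, and the across-probe LOA is 1.96·√(2(29.3 + 25)) = 20.4%.

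**Length, results exactly at the limits.** w = 10/(1.96·√2) = 3.61%, and √(b² + s²) = 3.61 × √(0.93/0.07) = 13.15%.

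| Measure | Assumed s | Observed ICC; LOA | Common-probe ICC | Across-probe ICC | Across-probe LOA |
|---|---|---|---|---|---|
| Elasticity | 2% | 0.90; ±15% | 0.899 | 0.886 | ±16.0% |
| Elasticity | 5% | 0.90; ±15% | 0.891 | 0.815 | ±20.4% |
| Elasticity | 10% | 0.90; ±15% | 0.848 | 0.559 | ±31.5% |
| Length | 2% | 0.93; ±10% | 0.928 | 0.908 | ±11.4% |
| Length | 5% | 0.93; ±10% | 0.919 | 0.796 | ±17.1% |
| Length | 10% | 0.93; ±10% | 0.849 | 0.392 | ±29.5% |

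**Simulation check.** 10 women, 2 readings each, 10,000 runs, with assumed b = 12.8% and w = 5.41%. The probe effect was either an additive offset or a proportional gain error.

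| Probe effect | s | Median same-probe ICC | Chance that estimated ICC ≥ 0.90 | Mean LOA half-width |
|---|---|---|---|---|
| Additive | 0% | 0.849 | 0.256 | 14.93% |
| Additive | 5% | 0.866 | 0.318 | 14.99% |
| Additive | 10% | 0.899 | 0.491 | 15.26% |
| Proportional | 0% | 0.846 | 0.250 | 14.99% |
| Proportional | 5% | 0.864 | 0.311 | 14.97% |
| Proportional | 10% | 0.898 | 0.489 | 15.02% |

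The direction agrees with the formulas. The LOA are unchanged for a gain error on the percent scale, and move slightly for an additive offset because the percent denominator changes. That is why the probe effect is essentially, not exactly, absent from the LOA.

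**The case against.** **The premise joins two sections.** No sentence says that the disposable measuring part carrying the sensors is the single-use shaft. The Introduction describes a concept in the future tense, and Protection Against Risks says that no voltage is supplied to the probe, which leaves its construction open. This stands as a condition: full confounding of sensor and woman is the natural reading, not a documented fact.

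**One insertion may not be settled.** Subjects speaks of two CM measurements per woman, whereas the procedure yields six readings (four sites and two repeats), and the procedure may be optimised later. But no section mentions a second insertion or a second probe, and the procedure has one removal, at the end.

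**The end points measure what they are labelled.** For same-probe intraoperator repeatability, the paired-difference LOA and the ICC are valid. A reader might infer that the end points are wrong in themselves, and the documents do not support that. What remains is narrower: the label does not state same probe and same insertion, and the protocol elsewhere claims reproducibility.

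**The size is assumed throughout.** At a 2% probe CV the gain over a common-probe ICC is negligible (0.900 against 0.899). With a between-woman CV of 20% and w = 5.41%, the observed ICC already passes without any probe variation (400/429.3 = 0.93) and reaches only 500/529.3 = 0.94 at a 10% probe CV. A reader might infer that a pass in this trial would be an artefact, but nothing in the documents shows that.

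**The link to the study in pregnant women is inferred.** A reader might take end points 2 and 3 as the gate to that study. The protocol refers only to unspecified research milestones. Its explicit condition is that risks are first assessed in non-pregnant women.

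**Conclusion.** The point holds, on condition that the sensors are on the single-use part. End points 2 and 3 can then support only same-probe, same-insertion, intraoperator repeatability. They cannot support the reproducibility named in Importance of the Knowledge to be Gained, or agreement between visits that use different probes.

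The direction follows from the variance formulas. The size cannot be found from the documents. Under the assumed values, the effect is small at a probe CV of 2% and material from about 5%, and at 10% a result that just meets the elasticity limits would correspond to an across-probe LOA about twice as wide as the one reported (31.5/15 = 2.1). The figures rest on independent, roughly normal probe effects and repeat errors, and on observed results exactly at the limits. The claim needs to change, not the examination.

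**What to change.** 1. Reword end points 2 and 3, and the aim in Importance of the Knowledge to be Gained, to same-probe, same-insertion, intraoperator repeatability. State that they do not show agreement between probes or visits. Confirm whether the single-use shaft carries the sensors.

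2. During the bench testing already planned, take at least two replicate readings per probe on a common simulator model, arranged so that sterility at clinical use is kept. Record the probe identifier on the case report form. Single readings would not do: their spread mixes probe variance with bench repeat error, and adding the within variance to it would count repeat error twice.

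3. Estimate the probe variance net of bench repeat error and report it with a confidence interval. Beside end points 2 and 3, give the across-probe LOA = ±1.96·√(2(within variance + probe variance)), on the percent scale, as a descriptive figure and not a success criterion.

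Cost: with one probe for each of 10 women, 10 × 2 = 20 bench readings for each of elasticity and length, one form field and a wording change. There is no added procedure for the women. The downsides are a narrower claim and an imprecise, possibly less favourable, across-probe LOA. With 10 probes, the 95% interval for the SD runs from roughly 0.7 to 1.8 times the estimate, and somewhat wider once bench error is subtracted. Readings taken before sterilization would also miss any shift in calibration that sterilization causes, which the report should state.

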## Study Objectives

The objectives of the Phase I pilot clinical study are:

1. To assess potential risks of CM to pregnant women and fetuses in a study with non-pregnant women,
2. To verify proposed data collection and examination techniques, and
3. To assess device performance, measurement repeatability and usability.

## Study Description

### Study Timeframe

December 1, 2016 – February 28, 2017.

### Sample Size

The study will involve 10 remunerated subjects.

### Clinical Site

The study will be conducted at Princeton Urogynecology, Princeton, NJ.

### Subjects

The study will involve 10 non-pregnant, 2 CM measurements per subject. Adult non-pregnant pre-menopausal women scheduled for a regular gynecological examination at Princeton Urogynecology (Princeton, NJ) will be considered eligible for enrollment into the study. Each patient will first be studied with the existing clinical means and then with the CM. A clinical research assistant will maintain a log as to any concerns/complications with the CM.

## Enrollment

Conditions precluding patients from participation are listed in the study exclusion criteria below. In addition, cognitively impaired patients will not be asked to participate. No patients will be excluded on the basis of race. Adult women in reproductive age (21-44 years) will be included.

### Inclusion criteria

1. Adult women age 21-44 years
2. Non-pregnant women

### Exclusion criteria

1. Active cancer of the colon, rectum wall, cervix, vaginal, uterus or bladder
2. Ongoing or prior radiation therapy for abdominal or pelvic cancer
3. Recent (less than four months) pelvic surgery
4. Surgically absent uterus, rectum or bladder
5. Significant circulatory or cardiac conditions that could cause excessive risk from the examination as determined by attending physician
6. Severe abdominal or pelvic adhesions preventing access to pertinent anatomy
7. Known or suspected bleeding disorder
8. HIV or hepatitis B positive serology
9. Warty lesions on the vulva
10. Extensive varicose veins on the vulva
11. Active skin infection or ulceration within the vagina/vulva (Herpes infection)
12. Presence of a vaginal septum
13. Severe hemorrhoids

## Data Collection

Cervix tissue elasticity and length measurement data as well as patient age, weight, height and parity, patient questionnaire (CM scan comfort, pain).

## Device

Cervix Monitor (CM)

## **Assignments**

Informed Consent Form (ICF) and authorization to release privacy data (HIPAA) Form will be obtained from the subject prior to surgery. Clinical investigator will follow the IRB approved informed consent process to answer all questions and provide explanations during enrollment to about the study.

## **Methods and Procedures**

The examination procedure will comprise the steps of:

1. Inserting the speculum into the vagina to provide appropriate visualization and access to the cervix.
2. Performing CM measurements at 3, 6, 9, and 12 o'clock specifying the probe tip location on cervix on the touch screen display.
3. Review the measurement results (elasticity and length values) and repeat two measurements, one at the location with the lowest elasticity and one at the location with highest value.
4. Removing the probe and speculum from the vagina.

This CM examination procedure will be explored and further optimized based on the practical experience.

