## **Data Analysis**

Measurement repeatability between two measurements will be assessed with a reliability parameter, which is also known as an intraclass correlation (ICC), as it equals the correlation between any two measurements made on the same subject. The difference between pairs of measurements will be plotted against their mean in a Bland-Altman plot. The average difference between measurements will be calculated as well as the 95% limits of agreement (LOA).

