### Source of Materials

Upon patient's consent, relevant clinical and demographical data will be collected. Specifically, obstetrical history, course of the previous current pregnancy(s), history of prior surgery and a connective tissue disorders (i.e. Ehlers-Danlos Syndrome, Benign Joint Hypermobility Disorder, etc.), race, age, height, weight, and parity will be documented.

Prior to taking the CM scan, standard obstetric external and internal vaginal examination will be performed by a clinical investigator. Attention to cervix softness, elasticity and any abnormalities

will be made and the results recorded to map the cervix surface. A 4-point grading system for cervix elasticity would be giving soft (0), or moderately soft (1), or moderately stiff (2), or stiff (3) elasticity scores to cervix. These subjective measurements would then be correlated with the CM data for agreement or discordance.

The CM examination will be performed as described above in Methods and Procedures section. The process is quick, non-invasive and should cause no additional discomfort to the patient as compared to a standard pelvic examination. All results will be recorded using an examination chart, which will be a part of the Case Report Form (CRF) specifically designed for the study. The chart will summarize all findings by all mean to characterize the cervix in terms of appearance and elasticity.

All necessary clinical and demographic data will be derived from existing records and de-identified. No additional clinical tests will be ordered to support this research. A specific clinical study number will be generated for each examination case so the link between the data and the patient will be created without revealing patient identity.

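### The first readings are reviewed before the repeats and nothing masks them, so ICC and LOA could look better than with masked repeats; direction only, and the effect may be nil

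*Combined protocol and SAP*

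**What the plan says.** Methods and Procedures, step 2, takes four readings, at 3, 6, 9 and 12 o'clock, with the operator "specifying the probe tip location on cervix on the touch screen display". Step 3 then reads "Review the measurement results (elasticity and length values) and repeat two measurements", one at the site of lowest and one at the site of highest elasticity. The probe and speculum come out only in step 4, so first readings, review and repeats belong to one examination.

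Data Analysis describes the ICC in the words "as it equals the correlation between any two measurements made on the same subject" and adds a Bland-Altman plot, the mean difference and 95% LOA. Study End Points, item 2, sets the elasticity limit: "The CM elasticity measurements have intraoperator ICC of 0.90 or above; 95% LOA is within" ±15%. Item 3 sets 0.93 and ±10% for cervix length. These are the study's only numerical success limits.

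Subjects gives "2 CM measurements per subject", which does not match four readings plus two repeats. No section covers the values, gives the choice of sites to a second person, or says which value counts if a reading is taken again.

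**The concern.** A repeatability study needs a second reading that owes nothing to the first. Here the first numbers, length included, are looked at just before the repeat is taken. An operator who knows the target could, without intending to, adjust contact, angle or pressure, or take a discordant reading again. Any such pull shrinks the paired differences, which raises the ICC and narrows the LOA.

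At stake are the only two numerical endpoints. Importance of the Knowledge to be Gained places the studies in pregnant women after the milestones of this stage are met. If a pull were present, no later analysis of the stored values could separate it from true repeatability, so the protection has to be in place before data collection.

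**Working it through.** **What the text establishes**

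| Link in the argument | What the documents give |
|---|---|
| Review comes before the repeats | Stated in step 3 |
| Values are not masked | No section masks them |
| The operator sees the values | Not stated. Study End Points calls the ICC intraoperator, and Protection Against Risks speaks of results being shown to the user during the examination |
| These repeats form the analysed pairs | Not stated. Step 3 is the only repeat described |
| A seen value can pull the repeat | Not shown |

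**Direction.** The plan gives no figure to reproduce: N = 10 comes with no assumed ICC, error or precision. Assume that a masked repeat y is recorded as x + (1−f)(y−x), where x is the first reading and f the fraction of pull. The difference becomes (1−f)(y−x), so the LOA shrink by (1−f). That factor follows from the assumed model and is not evidence about this device. A masked LOA of ±20% reaches ±15% when 1−f = 15/20, so f = 0.25.

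For the ICC, set the total variance to 1 and the masked ICC to r. Then MSW = (1−f)²(1−r), MSB = 2r + (1−r)(1+f²), and ICC = (MSB−MSW)/(MSB+MSW). With r = 0.85:
- f = 0: (1.85 − 0.15)/(1.85 + 0.15) = 0.85
- f = 0.10: (1.8515 − 0.1215)/(1.8515 + 0.1215) = 0.877
- f = 0.25: (1.8594 − 0.0844)/(1.8594 + 0.0844) = 0.913

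**Simulation of step 3, elasticity only.** The documents give 10 women, four sites, repeats at the lowest and highest observed site (20 pairs) and the limits 0.90 and ±15%. Assumed: nominal mean 100; woman SD and site SD both 5, 10 or 15%; error CV 4, 7 or 10%; and f. Differences are in percent of the pair mean, and LOA are the mean difference ± 1.96 SD. At CV 7% and SD 10%:

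| f | Median LOA half-width | Median ICC | Chance of meeting both limits |
|---|---|---|---|
| 0 | 20.8% | 0.83 | 1% |
| 0.10 | 18.7% | 0.86 | 4% |
| 0.25 | 15.6% | 0.90 | 22% |
| 0.33 | 13.9% | 0.92 | 44% |

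The pass chance depends almost wholly on the assumed inputs. At CV 4% and SD 10% it is already 80% with f = 0. At CV 10% it is at most about 2% in every cell, pull or no pull. Length was not simulated.

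**Choice of the extreme sites, with no pull (f = 0).** Compared with two fixed sites at CV 7%, the median LOA go from 19.3 to 21.2% (SD 5%; 21.2/19.3 = 1.10), 19.6 to 20.8% (SD 10%; 1.06) and 20.4 to 21.4% (SD 15%; 1.05). Over all combinations run they are about 3 to 12% wider. The median ICC rises as well, for example from 0.80 to 0.83 at SD 10% and from 0.90 to 0.92 at SD 15%. At CV 4% and SD 10% the chance of meeting both limits rises from 67% to 80%.

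**The case against.** The harm needs two links that the documents do not supply.

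First, step 3 must provide the analysed pairs. The count in Subjects could also mean two complete examinations per woman, and the 20 modelled pairs would then not be the analysis. This stands as an uncertainty. It is also a reason to name the pairs in the plan.

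Second, the operator must be able to move a value that the device computes. The Introduction says "Both stress and strain data will allow cervix elasticity and effacement evaluation"; these are sensor data, not a judged score. This stands too: f may be zero, and at f = 0 nothing is gained.

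It is also fair that this is a 10-woman pilot meant to try out the examination technique, that the procedure is expected to be optimized, and that patient management does not change. All of this lowers the weight of the point. It does not remove it, because the plan itself makes the ICC and LOA its success limits.

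Two stronger readings are tempting. A reader might infer from the pass chances that the study is likely to succeed falsely, but they run from near 0 to near 100% on inputs that the documents do not give, so none should be carried forward. A reader might also infer that the extreme sites cancel the bias because they widen the LOA. They also raise the ICC, so the offset is not reliable.

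**Conclusion.** The point holds as a gap in protection against bias, not as an error or a contradiction. The order of steps and the absence of masking are plain in the text. That one operator sees the values, and that the step 3 repeats are the analysed pairs, is the natural reading but is not stated. On that reading the ICC and LOA could look better than with masked repeats, and the data could not reveal it.

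Only the direction is supported. The size is unknown and may be nil. A reader might infer that the device's repeatability will be overstated; the documents do not support that, because nothing in them shows that a reading can be steered. The choice of lowest and highest sites should be judged separately. This is a cheap, optional improvement.

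**What to change.** Reorder step 3:

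1. Cover the numeric values from the operator until all six readings are stored, leaving location marking on the touch screen usable.
2. Let the research assistant read the values and name the two repeat sites in clock order, without giving values or saying which site is lowest or highest.
3. Move the review of results to after the last reading, so that on-screen review is still tried out.
4. State in Data Analysis that each pair is the first stored reading at the selected site and the first stored repeat there.
5. Allow a re-take only for a technical fault recorded in the CRF before the operator sees the value. The re-take then replaces the faulty reading in the pair, the original is kept, and the analysis is also shown with the original.

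The cost is one reordered step, a CRF line and a sentence in Data Analysis. There are downsides:
- The operator's plausibility check is delayed.
- The assistant, whose stated task is "A clinical research assistant will maintain a log as to any concerns/complications with the CM", takes on a new task and needs brief training.
- How the values can be covered depends on a screen layout that the documents do not describe.
- Masking is only partial. The operator knows that the two sites are the extremes, and the cervix has already been palpated: "Prior to taking the CM scan, standard obstetric external and internal vaginal examination will be performed by a clinical investigator".
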